8.4.3. Other Restrictions

Subjects will be instructed to maintain their normal caffeine intake as well as normal activity/exercise throughout the study. Subjects are prohibited from participating in a weight management program for the duration of the study.

8.4.4. Pain Management

Because ALKS 3831 contains samidorphan, a μ -opioid receptor antagonist, patients may experience reduced or ineffective analgesia when taking an opioid analgesic agent concurrently with ALKS 3831, including several days after last dosing of ALKS 3831.

In the event of an emergency, pain management of the subject should include the following:

- Regional analgesia or use of non-opioid analgesics
- If opiate anesthesia or analgesia is required, the subject should be continuously monitored, in an anesthesia care setting, by persons not involved in the conduct of the surgical or diagnostic procedure. The opioid therapy must be provided by individuals specifically trained in the use of anesthetic drugs and the management of the respiratory effects of potent opioids, specifically the establishment and the maintenance of a patent airway and assisted ventilation.
- Close monitoring by appropriately trained personnel in a setting equipped and staffed for cardiopulmonary resuscitation

For subjects requiring emergency opioid analgesics prior to dosing, the study drug should not be administered. If opioid analgesics are required after the study drug has been dosed, it may take several days for opiate sensitivity to be restored, since samidorphan is an opioid antagonist and could interfere with opioid-mediated pain management.

9. TREATMENT OF SUBJECTS

9.1. Study Drug Dose and Administration

Study drugs include samidorphan and matching placebo tablets, and olanzapine tablets, all for oral administration. Samidorphan is a Schedule II substance, and should be stored, dispensed, and otherwise handled in accordance with the associated regulations.

Olanzapine will be prescribed by the PI and will be dispensed for oral administration by study staff.

During the inpatient stays, study drug will be dispensed once daily, and the time of administration will be at the discretion of the clinic staff. Time of administration at any visit (inpatient or outpatient) may be adjusted as needed to accommodate post-dose measurements. Before being discharged from each inpatient stay, and at each outpatient post-randomization study visit until Visit 23/ET, all subjects will receive blister cards containing samidorphan or placebo for self administration. Subjects will be instructed to take 2 tablets per day from the blister card and their olanzapine tablet(s) once daily in the evening or at bedtime until Visit 23. The subject will take the final samidorphan dose the night before Visit 23. No samidorphan dose will be administered onsite during Visit 23/ET. Olanzapine dosing will continue uninterrupted. Two safety follow-up visits will occur 2 and 4 weeks after Visit 23. Any subject who prematurely discontinues from the study during Part B will be asked to return to the clinic for an ET visit and follow-up visits 2 and 4 weeks after the ET visit.

Subjects should take all study drug tablets (olanzapine and samidorphan/placebo) orally and at the same time. Subjects should be advised that somnolence may occur with dosing and thus they should avoid driving or operating heavy machinery until they have determined how the study drug affects them.

Subjects will be instructed to keep all unused tablets in their blister card and not to mix tablets between blister cards and bottles. Subjects will also be instructed to return unused tablets to the site when they return for their next visit. If dosing occurs at this visit, the dose should be taken from subjects' next blister card. The dose should not be taken from the blister card the subjects are returning.

If a dose is missed or forgotten, subjects will be instructed to resume the regular dosing schedule the following evening. Subjects will be instructed not to take a double dose to try to "make up" for a missed dose.

9.2. Treatment Compliance

As described in [Section 8.3.22](#), study personnel will assess treatment compliance at every visit from first dose of study drug at Visit 2 through Visit 23/ET accounting for the dispensed tablets (samidorphan, olanzapine, and placebo accounting for dosed, lost/missing, or remaining tablets). Additional measures of compliance may be used; these will be described in the Operational Plan as necessary. Study drug accountability will be performed using an EDC system. Subjects who have demonstrated compliance during the first week of olanzapine study will be randomized to double-blind treatment (samidorphan or placebo).

Noncompliance will be discussed with the subject as needed.

9.3. Randomization and Blinding

Part A of this study will be conducted in a double-blind fashion. On Day 8 (Visit 3), subjects will be randomized to receive one of the following regimens in a 1:1:1:1 ratio:

- Olanzapine + Samidorphan (5 mg)
- Olanzapine + Samidorphan (10 mg)
- Olanzapine + Samidorphan (20 mg)
- Olanzapine + Placebo

Randomization will be performed centrally through an IWRS system and will be stratified by the amount of weight change during the olanzapine lead-in period (ie, from Day 1 to Day 8), with subjects grouped into the following 3 strata:

- Weight change ≤ 0 kg
- Weight increase >0 to <1 kg
- Weight increase ≥ 1 kg

Alkermes staff, clinical staff, and subjects will remain blinded to treatment assignment until Part A of the study is complete. All ^{PPD} staff will remain blinded except when their study function requires unblinding (eg, drug supply management, IWRS operation, DSMB operation, etc). These unblinded staff will follow procedures designed to ensure that study integrity is maintained.

9.4. Breaking Study Blind

The PI is responsible for all trial-related medical decisions. Emergency unblinding may be done without contacting a medical monitor. Any premature unblinding should be promptly documented and explained to the medical monitor within 24 hours following disclosure of study drug assignment. Breaking the blind for a single subject will not affect the blind for the remaining subjects.

Once Part A of the study is complete (ie, the final subject has completed the final Part A assessment), the Part A data will be locked, unblinded, and the Part A data analyses will be conducted. This may occur prior to the completion of Part B of the study; however individual treatment assignments will remain blinded to the sites.

10. STUDY DRUG MATERIALS AND MANAGEMENT

10.1. Study Drug

Commercially available olanzapine will be supplied or arranged for dispensing by the investigative site.

Samidorphan will be provided by the sponsor. Each tablet contains 2.5, 5, or 10 mg. Subjects will take 2 tablets per day (ie, doses of samidorphan will be 5, 10, or 20 mg) by mouth.

Samidorphan is a Schedule II substance and will require proper handling, storage, and accountability in accordance with local, regulations, and operating procedures.

Placebo consists of tablets, identical in size and appearance to the samidorphan tablets. Subjects will take 2 tablets per day by mouth.

10.2. Packaging and Labeling

Samidorphan and placebo will be packaged in blister packs. Blister packs will be provided in weekly or biweekly configurations. The weekly blister pack will contain 18 tablets, which provides one week of dosing with sufficient coverage to allow for 2 additional once daily doses. The biweekly packs will contain 32 tablets, providing 2 weeks of dosing with sufficient coverage to allow for 2 additional once daily doses.

Blister pack labels will meet all applicable local and regulatory requirements.

10.3. Storage

Under the US Controlled Substances Act, samidorphan is considered a Schedule II substance because it is derived from opium alkaloids. Therefore, samidorphan and/or blinded study drug must be stored in accordance with restrictions related to Schedule II substances. The site will take adequate precautions, including storage of the investigational drug in a securely locked, substantially constructed cabinet, or other securely locked, substantially constructed enclosure, access to which is limited, to prevent theft or diversion of the substance.

10.4. Accountability

The clinical site is required to maintain current drug dispensation and accountability logs throughout the study. All unused supplies will be checked against the drug movement records during the study and/or at the end of the study.

Refer to [Section 9](#) for additional study drug reconciliation procedures.

10.5. Handling and Disposal

Following completion and verification of accountability logs, all unused and used packages must be destroyed in accordance with regulations for controlled substances. Study drug destruction will occur only at the end of the trial and upon notification/approval by the sponsor. Packages may be destroyed on site according to Good Clinical Practice (GCP), site procedures and in accordance with all regulations for controlled substances. Alternatively, the sponsor may arrange

for destruction with a third party vendor operating in accordance with GCP. Redispensation or disposal of drug product during the course of the trial is prohibited.

11. ASSESSMENT OF EFFICACY

11.1. Primary Endpoint

The primary endpoint is the absolute change in PANSS total score from randomization to the end of Part A.

11.2. Secondary Endpoints

- Percent change in body weight
- Absolute change in body weight
- Proportion of subjects exhibiting significant weight gain (definition of weight gain will include body weight gain greater than 7%)
- Absolute change in CGI-S

11.3. Additional Endpoints

- Change in waist circumference
- Change in IWQOL-Lite scales (physical function, self-esteem, sexual life, public distress and work) and total score
- Change in PSP
- Change in FCI
- Change in alcohol and drug use

12. PHARMACOKINETIC/ PHARMACODYNAMIC ASSESSMENTS

For all subjects, samidorphan, RDC-9986 (primary metabolite of samidorphan) and olanzapine concentrations will be determined from plasma samples collected according to the schedule in [Table 1](#) and [Table 2](#). PK data may be used to assess compliance with study drug administration and/or included in a subsequent population PK analysis conducted outside of this study.

13. ASSESSMENT OF SAFETY

Safety will be assessed from randomization to the end of Part A. Part B data will be used to examine longer-term safety. The number and percentage of subjects with AEs from randomization to the end of Part A is included as a secondary endpoint. In addition to this secondary endpoint, safety will be evaluated based on AEs, vital signs, clinical laboratory assessments (hematology, blood clinical biochemistry, and urinalysis), 12-lead ECG findings, and data from C-SSRS surveys.

13.1. Safety Endpoints

- Number and percentage of subjects with adverse events from randomization to the end of Part A
- Change in blood lipid concentrations including LDL, HDL, total cholesterol and triglycerides
- Change in assessments related to glucose regulation including fasting glucose and insulin, fasting glucose to fasting insulin ratio, HbA1c, c-reactive protein, leptin and bicarbonate
- Change in vital signs including blood pressure

13.2. Definition of Adverse Event

An AE is any untoward medical occurrence in a patient or clinical investigation subject administered a pharmaceutical product. The occurrence, which may or may not have a causal relationship with the investigational treatment, may include any clinical or laboratory change that does not commonly occur in that subject and is considered clinically significant.

Illnesses present prior to the subject signing the main ICF are considered to be pre-existing conditions and are documented on the medical history eCRF. Pre-existing conditions that worsen during the study are entered on the AE eCRF.

All out-of-range laboratory values will be deemed as clinically significant or not clinically significant by the PI (or designated investigator). Clinically significant values will be considered AEs and recorded as such on the eCRFs.

13.3. Definition of Serious Adverse Event

A serious adverse event (SAE) is any AE, occurring at any dose and regardless of causality that meets one or more of the following criteria:

- Results in death
- Is life-threatening. The subject is at immediate risk of death from the reaction as it occurs. This does not include reaction that, had it occurred in a more severe form, might have caused death.

- Requires inpatient hospitalization or prolongation of existing hospitalization. Hospital admission for elective surgery scheduled prior to study entry is not considered an SAE.
- Results in disability/incapacity (eg, a substantial disruption of a person's ability to conduct normal life functions)
- Is a congenital anomaly/ birth defect

Important medical events that may not result in death, be immediately life threatening, or require hospitalization may be considered SAEs when, based upon appropriate medical judgment, they may jeopardize the patient or subject and may require intervention to prevent one of the other outcomes listed above.

At Visits 3 and 13, subjects are admitted for a 2-night inpatient stay at the study site, per the protocol. If prolongation of this protocol-required stay is necessary for the management of the subject's schizophrenia **without a worsening of the subject's baseline clinical status or the development of new signs or symptoms**, and is confirmed as such by the medical monitor, the event should be categorized as an AE, not an SAE.

Admission to an inpatient unit or hospital for a non-medical reason (ie, social-stay admission) during the trial is considered an AE, not an SAE.

13.4. Relationship to Study Drug

The assessment of study drug relationship to each AE will be reported on the appropriate source document (and SAE form, in the event of an SAE) by the PI (or designated investigator) according to his/her best clinical judgment. The criteria listed in [Table 4](#) should be used to guide this assessment. Please note that not all criteria must be present to be indicative of a particular drug relationship. All study drugs are considered "test drugs" for the purposes of the definitions listed in the table. However, relationship and action taken will be separated out in the EDC to assess for olanzapine and samidorphan/placebo separately. The PI (or designated investigator) can attribute relationship to olanzapine, samidorphan/placebo or both.

Table 4: Causality Guidelines

Relationship¹	Criteria for assessment
Definitely related	
There is evidence of exposure to the test drug. AND The temporal sequence of the AE onset relative to administration of the test drug is reasonable. The AE is more likely explained by the test drug than by another cause. Dechallenge (if performed) is positive. Rechallenge (if feasible) is positive. The AE shows a pattern consistent with previous knowledge of the test drug or test drug class.

Probably related	
There is evidence of exposure to the test drug. AND The temporal sequence of the AE onset relative to administration of the test drug is reasonable. The AE is more likely explained by the test drug than by another cause. Dechallenge (if performed) is positive.

Possibly related	
There is evidence of exposure to the test drug. AND The temporal sequence of the AE onset relative to administration of the test drug is reasonable. The AE could have been due to another equally likely cause. Dechallenge (if performed) is positive.

Probably not related	
There is evidence of exposure to the test drug. AND There is another more likely cause of the AE. Dechallenge (if performed) is negative or ambiguous. Rechallenge (if performed) is negative or ambiguous.

Definitely not related	
The subject did not receive the test drug. OR Temporal sequence of the AE onset relative to administration of the test drug is not reasonable. OR There is another obvious cause of the AE.

¹ Relationship will be assessed twice: once for olanzapine and once for samidorphan/placebo

13.4.1. Adverse Events of Special Interest

PIs or their designees will be required to record additional details for AEs of special interest related to abuse liability. These AEs fall into general categories including (but not limited to)

substance-related disorders, euphoria, sedation, stimulation, hallucinations, motor impairment, and cognitive impairment. More details on these AEs will be provided outside of this protocol.

13.5. Monitoring and Recording of Adverse Events

AE data collection will begin after a subject signs the main ICF and will continue until completion of the safety follow-up visit. Any AE or SAE having an onset after the safety follow-up visit will not be collected or reported unless the PI (or designated investigator) feels that the event may be related to the study drug.

Subjects will be instructed by the PI (or designee) to report the occurrence of any AE. All volunteered, elicited, and observed AEs are to be recorded on the AE eCRFs.

The PI (or designated investigator) will assess all AEs regarding any causal relationship to the study drug (see Section 13.4), the intensity (severity) of the event, action taken, and subject outcome.

The following criteria should be used to guide the assessment of intensity (severity):

- **Mild:** Causes awareness of sign or symptom, but is easily tolerated; does not interfere with usual activities
- **Moderate:** Causes discomfort enough to interfere with usual activities
- **Severe:** Is incapacitating; results in inability to work or perform usual activities

All AEs will be followed until resolution, until deemed stable by the PI, or until the subject is deemed by the PI to be lost to follow-up.

For clinical study safety reporting purposes, the most recent version of the IB will be used as the reference document to designate event expectedness.

Withdrawal from the study as a result of an AE and any therapeutic measures that are taken shall be at the discretion of the PI (or designated investigator). If a subject withdraws from the study for any reason, any ongoing AEs will be followed until resolution, until deemed stable by the PI, or until the subject is deemed by the PI to be lost to follow-up.

13.6. Reporting of Serious Adverse Events

All SAEs must be reported to PPD [redacted] within 24 hours of discovery, by faxing the report to the following:

Attention: PPD [redacted] Medical Monitor

US Fax Number: PPD [redacted]

EU Fax Number: PPD [redacted]

The written report should be submitted on the SAE form provided for this purpose. The report must include the PI's (or designated investigator's) opinion as to whether the event is study drug-related. If this relationship is determined to be possibly, probably, or definitely related to study drug, evidence to support this assessment must also be provided. This assessment will be done twice: once for olanzapine and once for samidorphan/placebo. The report submitted will include both assessments.

14. STATISTICS

14.1. Sample Size Considerations

Sample size calculations are based on the primary endpoint of absolute change in PANSS total score. These calculations assume an equivalence margin of 10 points, a standard deviation of 20 points, and a true difference of 0 points. With these assumptions, 280 randomized subjects provide 95% power to demonstrate equivalence on the primary endpoint (absolute PANSS total score change from randomization to the end of Part A) with a 2-sided test at an alpha level of 0.05. These 280 subjects represent 70 subjects for each treatment arm (ALKS 3831 5 mg, ALKS 3831 10 mg, ALKS 3831 20 mg, and placebo) in a 1:1:1:1 ratio. For the primary analysis, subjects in the 3 ALKS 3831 treatment groups will be pooled for comparison with placebo. If this analysis shows equivalence, follow-up analyses on individual dose levels will be performed. Assuming a 20% discontinuation rate prior to randomization, an estimated 350 subjects will be enrolled in this study.

14.2. General Statistical Methodology

The statistical analysis methods are described below. Additional details will be provided in the statistical analysis plan to be finalized before database lock and unblinding. In general, summary statistics, including n, mean with (SD), median, minimum, and maximum for continuous variables and number (%) of subjects in each category for categorical variables will be provided by treatment group for all variables.

Source data for the summary tables and statistical analyses will be presented as subject data listings.

All statistical tests and CIs, unless stated otherwise, will be 2-sided and will be set at $\alpha = 0.05$.

14.2.1. Efficacy Population

The efficacy analysis will be conducted on 2 analysis populations:

- The FAS 1 population will include all subjects who are randomized, receive at least one dose of study drug, and have at least one post-baseline PANSS assessment.
- The FAS 2 population will include all FAS 1 subjects who gained weight during the initial week of olanzapine treatment prior to randomization and have at least one post-baseline weight assessment.

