This is Alkermes' first study of the co-administration of olanzapine and samidorphan in a population of adults with schizophrenia. In addition, this study includes higher doses of samidorphan than the 5-mg dose that was used in a prior study (ALK33-301). Samidorphan has been associated with somnolence, and olanzapine has been associated with orthostatic hypotension. In ALK33-301, there was no apparent additive effect of the co-administration on either of these adverse effects. However, because the current study involves higher doses of samidorphan than studied previously, it was desired to take a conservative approach by monitoring subjects in an inpatient setting for 2 nights following randomization (Visit 3) and transition (Visit 13).

During clinic visits, assessments of psychotic symptoms using measures such as the PANSS and CGI-S will occur. Body weight will be measured using consistent methods at every visit. Alcohol and drug use will be monitored throughout the study. Concentrations of samidorphan, RDC-9986 (primary metabolite of samidorphan), and olanzapine will be determined in plasma samples collected at Visits 2-23.

8.1.1. Part A (Screening, Olanzapine Lead-In, and Double-Blind Placebo-Controlled Treatment Period)

Screening assessments will occur in the 30-day period before subjects report to the clinic for verification of eligibility and initiation of olanzapine treatment (Study Day 1). On Study Day 1 (Visit 2), all eligible subjects will be initiated on olanzapine. Olanzapine dose will be selected and titrated by the PI based upon individual subject needs and consistent with current clinical practice. Subjects will return one week later (ie, Study Day 8, Visit 3) for a 2-night inpatient stay and the start of the 12-week double-blind placebo-controlled treatment period. At this visit, subjects will be randomized in a 1:1:1:1 ratio to receive samidorphan (5 mg, 10 mg, or 20 mg) or placebo. Olanzapine dosing will continue uninterrupted. Thus, the Part A treatment groups will be as follows:

- Olanzapine + Samidorphan (5 mg)
- Olanzapine + Samidorphan (10 mg)
- Olanzapine + Samidorphan (20 mg)
- Olanzapine + Placebo

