8.3.8. Body Weight and Waist Circumference

Body weight will be measured 3 times at every visit. The median weight will be calculated by an Interactive Web Response System (IWRS) system at Visit 2 and Visit 3 to calculate the change in weight during the first week of olanzapine exposure. At Visit 2, as part of the eligibility assessment, the PI or designee must ensure that the subject's body weight has not changed by greater than 1 kg. Body weight will also be measured prior to discharge from the inpatient stay.

Subjects should be asked to void immediately prior to the body weight measurement. Subjects should be weighed on the same scale for each measurement under the same conditions. Subjects should remove all personal items, such as watches and jewelry, prior to body weight measurement. Subjects should be weighed in hospital gowns with a consistent amount of undergarments for each measurement. Subjects will be weighed 3 times. The median weight will be calculated by an IWRS system as described above at Visit 2 and Visit 3 and entered into an electronic data capture (EDC) system at all other visits.

Waist circumference will be measured according to the schedule shown in [Table 1](#) and [Table 2](#).

8.3.9. 12-Lead Electrocardiogram

A 12-lead ECG will be conducted according to the schedule shown in [Table 1](#) and [Table 2](#). For Part A, ECG will be measured anytime pre-dose and approximately 3 hours post-dose except for Visit 1 and Visit 2 where only 1 ECG will be done. For Visit 2, the ECG should be completed

before dosing. For Visit 6, dosing may be done earlier than normal to accommodate post-dose procedures.

For Part B, ECG will be measured anytime pre-dose and approximately 3 hours post-dose except for Visit 23/ET and Visit 24 where no dosing occurs. For Visit 16, dosing may be done earlier than normal to accommodate post-dose procedure.

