14.4. Efficacy Analyses

The primary endpoint is the absolute change in PANSS total score from randomization to the end of Part A (ie, the end of the 12-week, placebo-controlled double-blind treatment period) and will be evaluated by treatment group (ALKS 3831 vs. the placebo group [olanzapine alone]) using a 2-sided mixed-model for repeated measures (MMRM) to test for equivalence at an alpha level of 0.05. The primary analysis will be conducted in the FAS 1 population. More details about this analysis will be provided in the SAP.

The secondary endpoint, percent change in weight from randomization to the end of Part A, will be evaluated by treatment group using an MMRM approach similar to that of the primary endpoint. However, this will be a superiority analysis. Each treatment group will be compared to the placebo group with a 2-sided hypothesis test to test for superiority at an alpha level of 0.05. The secondary efficacy analysis will also be conducted in the FAS 1 population. More details about this analysis will be provided in the SAP.

Analysis of other secondary endpoints and additional endpoints will include inferential analyses and descriptive analyses by visit (mean, SD, median, minimum, and maximum for continuous variables and number and percent for categorical variables), as appropriate.

Analyses for the primary and secondary endpoints will be repeated in the FAS 2 population as sensitivity analyses when applicable. Additional details regarding these analyses will be provided in the SAP.

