3.2.2 Efficacy Populations

The efficacy analysis will be conducted on 2 analysis populations:

- FAS 1 Population is defined as all randomized subjects who received at least one dose of study drug and have at least one post-baseline assessment of PANSS total score.
- FAS 2 Population is defined as all FAS 1 subjects who gained weight during the first week of olanzapine treatment prior to randomization and have at least one post-baseline weight assessment.

FAS 1 population will be the primary efficacy population for analyses on all efficacy variables.

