3.6.2 Percent Change in Body Weight

The secondary endpoint, percent change in weight from randomization to Day 92, will be evaluated by treatment group using an MMRM approach similar to that of the primary endpoint. Pooled and individual ALKS 3831 treatment group will be compared to the placebo [olanzapine alone] group with a 2-sided hypothesis test to test for superiority at an alpha level of 0.05. The secondary efficacy analysis will be conducted in both FAS 1 and FAS 2 population. The MMRM model includes variables for the weight change strata in olanzapine lead-in period, treatment group, visit, and treatment group-by-visit interaction term as categorical fixed effect; baseline weight value will be included as a covariate.

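### The weight endpoints are analysed in sets that require a post-baseline PANSS, so a subject who leaves early with weights but no PANSS is in no planned weight efficacy analysis; the effect is probably small and the fix is cheap

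*Protocol*

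**What the plan says.** **Set definitions.** Protocol 14.2.1 admits to FAS 1 randomized subjects who "receive at least one dose of study drug, and have at least one post-baseline PANSS assessment". SAP 3.2.2 likewise requires that they "have at least one post-baseline assessment of PANSS total score". For the second set the protocol writes: "The FAS 2 population will include all FAS 1 subjects who gained weight during the initial week of olanzapine treatment", and adds that a post-baseline weight must exist. The weight condition is added to the PANSS condition and does not replace it.

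**Use for weight.** On percent weight change, Protocol 14.4 states: "The secondary efficacy analysis will also be conducted in the FAS 1 population". SAP 3.6.2 states: "The secondary efficacy analysis will be conducted in both FAS 1 and FAS 2 population". SAP 3.6.3 treats absolute weight change in a similar way. SAP 3.2.2 sets the general rule: "FAS 1 population will be the primary efficacy population for analyses on all efficacy variables".

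**Schedule.** Protocol 8.3.8 says: "Body weight will be measured 3 times at every visit". Protocol Table 1 places weighings on Day 9 (Visit 4) and Day 10 (Visit 5), during the inpatient stay that follows randomization on Day 8. In Part A, PANSS is scheduled at Visits 1, 2, 3, 6, 7, 9, 11 and 13, so the first post-baseline rating is on Day 15.

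**The concern.** Whether a subject counts in the weight comparison depends on whether a different instrument was administered after randomization. Weight alone would qualify almost everyone who was randomized and dosed, because the first post-baseline weighings fall within a required inpatient stay.

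No other planned analysis picks these subjects up. The synopsis lists body weight among the efficacy assessments. Weight is not among the analyses in SAP 3.7, so the Safety Population, which has no PANSS condition, supplies no weight comparison. The sensitivity analyses in SAP 3.6.2.1 either stay in FAS 1 and FAS 2 or name no other set.

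At stake is a post-randomization exclusion from the weight superiority analysis that serves no purpose for weight. Early departure could in principle depend on arm: Protocol 5.2.1 names nausea, fatigue and somnolence among the common events with samidorphan, and Protocol 8.1 added inpatient monitoring because doses exceed the 5 mg of the earlier combination study. The subjects concerned are the earliest dropouts, whom a robustness analysis should be able to include.

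**Working it through.** **Plan figures.** The documents give no weight effect, weight SD, weight power or rate of missing post-baseline PANSS, so no plan figure on this point can be reproduced. The only input is the sample size: 4 × 70 = 280 randomized, and 350 × (1 − 0.20) = 280, which agrees with the stated enrolment. The stated 95% power concerns PANSS and plays no part here.

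**Step 1: who falls in the gap.** The clearest case is a subject randomized on Day 8, weighed on Day 9 or on Days 9 and 10, who leaves before the Day 15 visit and has no PANSS at an ET visit. This subject has one or two post-baseline weights, is outside FAS 1 and is therefore outside FAS 2.

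**Step 2: how many, under assumption.** Let q be the share of the 280 with a post-baseline weight and no post-baseline PANSS. The number lost is 280q. If each lost subject carried full information, the standard error would grow by 1/√(1 − q). If a weight test had 80% power with all 280 (assumed), its power would be Φ((1.960 + 0.842)√(1 − q) − 1.960).

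| q (assumed) | Subjects lost | SE factor | Power, from 80% |
|---|---|---|---|
| 0% | 0 | 1.000 | 80.0% |
| 1% | 2.8 | 1.005 | 79.6% |
| 2% | 5.6 | 1.010 | 79.2% |
| 5% | 14 | 1.026 | 78.0% |
| 10% | 28 | 1.054 | 75.7% |

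These losses are upper bounds, because a weight from Day 9 or 10 says little about Day 92.

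**Step 3: which analyses move.**
- *MMRM contrast at Day 92 (SAP 3.6.2).* It uses observed data. A subject with only Day 9 and 10 weights informs the Day 92 contrast only through the within-subject correlation, so little changes.
- *Proportion with significant gain at Day 92 (SAP 3.6.4).* It uses observed values. A subject who left around Day 10 contributes nothing at Day 92 under either set.
- *By-visit weight summaries (SAP 3.6.2.1, 3.6.4).* Values at Days 9 and 10 exist for these subjects and are omitted.
- *LOCF ANCOVA (SAP 3.6.2.1, built as in 3.6.1.1).* It carries the most recent post-baseline value forward, so under a weight-based set these subjects would enter with their Day 9 or 10 weight.

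**Step 4: direction in the LOCF analysis.** Assume that leavers have zero weight change and that the others gain 3% on ALKS 3831 and 4% on olanzapine alone. Let a and b be the shares lost in those two groups. Ignoring covariates, the difference with FAS 1 is 3 − 4 = −1.00 percentage points. With all weighed subjects it is 3(1 − a) − 4(1 − b).

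| a (ALKS 3831) | b (olanzapine alone) | Calculation | Difference |
|---|---|---|---|
| 2% | 2% | 2.940 − 3.920 | −0.98 |
| 5% | 5% | 2.850 − 3.800 | −0.95 |
| 5% | 1.4% | 2.850 − 3.944 | −1.09 |
| 1.4% | 5% | 2.958 − 3.800 | −0.84 |

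Every input is assumed. The table shows only that inclusion can move the LOCF estimate either way.

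**The case against.** **The gap is narrow.** Part A dropouts are asked to return for an ET visit (Protocol 8.1.1). The ET column of Protocol Table 2 includes PANSS. SAP 3.11.1.3 treats an ET assessment within 7 days of the last samidorphan or placebo dose as on-treatment and maps it to Visit 6 if it falls on Days 9 to 18. Protocol 8.2 asks sites to reschedule missed visits. All this stands, and it is why the number is probably small. It need not be zero: subjects are asked and not obliged to return, and Protocol 7.3 expects the ET visit only when possible, with telephone contact as the fallback.

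**The weight superiority test is hardly touched.** This also stands. A reader might infer that the test is materially biased or weakened. The documents do not support that, because the specified contrast is at Day 92 and the subjects concerned have almost no information on Day 92.

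**Early dropout is not shown to differ by arm.** A reader might infer from the listed adverse events and the inpatient stays that it does. Protocol 5.3 reports that, apart from weight, samidorphan 5 mg did not appear to alter olanzapine's adverse event profile in healthy adults. Protocol 8.1 describes the stays as a precaution. Doses above 5 mg leave the matter open; they do not establish a difference.

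**Including these subjects does not make LOCF more correct.** LOCF would treat a Day 10 weight as a Day 92 outcome, so a larger difference under the wider set could be an artefact of carrying values forward. That is a limit of LOCF. It does not justify choosing subjects by PANSS.

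**One set gives one denominator.** This is a real convenience, and it is the only benefit of the present rule that the review could identify.

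**Conclusion.** The point holds as a defect in set definition with low expected impact. By the documents' own wording and schedule, a randomized, dosed subject with post-baseline weights and no post-baseline PANSS is excluded from every planned weight efficacy analysis, including those in FAS 2, which carries its own weight condition.

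The number affected cannot be derived. An assumed 1% to 5% means about 3 to 14 of 280, and ET capture could bring it close to zero. The power loss at 5% is at most about 2 percentage points from an assumed 80%. On selection, dropping 5% of an arm whose mean differs by an assumed 0.5 SD shifts that arm's mean by 0.05 × 0.5 = 0.025 SD. The Day 92 MMRM and observed-case proportion should change little. The LOCF ANCOVA and early-visit summaries are affected more directly, with a direction that cannot be stated in advance. The change is worth making because it removes an exclusion unrelated to weight at almost no cost, not because a material error in the weight result has been shown.

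**What to change.** In Protocol 14.2.1 (and the synopsis, which repeats it) and SAP 3.2.2:

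- Define a weight analysis set: all randomized and dosed subjects with a baseline weight and at least one post-baseline weight, with no PANSS condition. The existing dosing condition need not change.
- Define FAS 2 as the subjects in that set who gained weight in the olanzapine lead-in.
- Keep the PANSS condition for the PANSS analyses only.
- Point Protocol 14.4 and SAP 3.6.2 to 3.6.5 to the new set for percent change, absolute change, significant weight gain and their sensitivity and subgroup analyses, and amend the general rule in SAP 3.2.2 to match.
- Report in the disposition table how many subjects are in the weight set and not in FAS 1, by arm, so that the size of the gap is visible.

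Cost: short text edits, one extra population flag and denominators that may differ slightly between weight and PANSS. Data collection and the primary PANSS analysis are unaffected.
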